6.1.2.1. Within Vaccine Group

For the ACWY1d, ACWY2d, Co-ad, and PCV13 vaccine groups, at each time point that data on meningococcal antibody titers, antipneumococcal antibody concentrations, or pneumococcal antibody titers are available:

- Percentages of subjects with rSBA-MenA, rSBA-MenC, rSBA-MenW-135, and rSBA-MenY titers $\geq 1:8$ and $\geq 1:128$ will be calculated.
- Percentages of subjects with hSBA-MenA, hSBA-MenC, hSBA-MenW-135, and hSBA-MenY titers $\geq 1:4$ and $\geq 1:8$ will be calculated.
- Percentages of subjects with anti-pneumococcal serotype 1, 3, 4, 5, 6A, 6B, 7F, 9V, 14, 18C, 19A, 19F, and 23F antibody concentrations $\geq 0.15\mu\text{g/mL}$, $\geq 0.26\mu\text{g/mL}$, and $\geq 0.35\mu\text{g/mL}$ will be calculated.
- Percentages of subjects with anti-pneumococcal serotype 1, 3, 4, 5, 6A, 6B, 7F, 9V, 14, 18C, 19A, 19F, and 23F OPA titers $\geq 1:8$ will be calculated.
- GMTs and GMCs with 95% CIs will be calculated.
- The distribution of antibody concentrations and titers will also be tabulated and evaluated using reverse cumulative distribution curves.

In addition, the following analyses will also be performed by country and by the number of doses of Prevenar 13 received before the study (2 or 3 doses):

- Percentages of subjects with rSBA-MenA, rSBA-MenC, rSBA-MenW-135, and rSBA-MenY titers $\geq 1:8$ and $\geq 1:128$ will be calculated.
- Percentages of subjects with hSBA-MenA, hSBA-MenC, hSBA-MenW-135, and hSBA-MenY titers $\geq 1:4$ and $\geq 1:8$ will be calculated.

- Percentages of subjects with anti-pneumococcal serotype 1, 3, 4, 5, 6A, 6B, 7F, 9V, 14, 18C, 19A, 19F, and 23F antibody concentrations $\geq 0.15\mu\text{g/mL}$, $\geq 0.26\mu\text{g/mL}$, and $\geq 0.35\mu\text{g/mL}$ will be calculated.
- Percentages of subjects with anti-pneumococcal serotype 1, 3, 4, 5, 6A, 6B, 7F, 9V, 14, 18C, 19A, 19F, and 23F OPA titers $\geq 1:8$ will be calculated.
- GMTs and GMCs with 95% CIs will be calculated.

6.1.2.2. Between Vaccine Groups

Confirmatory Primary Objectives

Noninferiority of MenACWY-TT when coadministered with Prevenar 13 versus MenACWY-TT given alone 1 month after vaccination.

- Two (2)-sided standardized asymptotic 95% CI of the vaccine group difference between the Co-ad and the Pool1d vaccine groups (Co-ad vaccine group minus Pool1d vaccine group) will be computed for the percentage of subjects with rSBA-MenA, rSBA-MenC, rSBA-MenW-135, and rSBA-MenY titer $\geq 1:8$ (Visit 2).

It can be concluded (for each meningococcal group separately) that coadministration of MenACWY-TT and Prevenar 13 is noninferior to administration of MenACWY-TT alone if the lower limit of the CI of the difference is greater than or equal to -10%.

Noninferiority of Prevenar 13 when coadministered with MenACWY-TT versus Prevenar 13 given alone 1 month after vaccination.

- 95% CI of the GMC ratio between the Co-ad and the PCV13 vaccine groups (Co-ad vaccine group over PCV13 vaccine group) will be computed for pneumococcal serotypes 1, 3, 4, 5, 6A, 6B, 7F, 9V, 14, 18C, 19A, 19F, and 23F (Visit 2). This will be performed using an analysis of covariance (ANCOVA) model on the \log_{10} transformation of the concentrations using the prevaccination \log_{10} transformation of the concentrations, the country, the number of doses of Prevenar 13 received before the study (2 or 3 doses), and the vaccine group as covariates.

It will be concluded (for each serotype separately) that coadministration of Prevenar 13 and MenACWY-TT is noninferior to administration of Prevenar 13 alone if the lower limit of the CI of the GMC ratio is above 0.5.

Exploratory Analysis

An exploratory evaluation of the comparability of the immune response to each pneumococcal serotype at 1 month after administration of Prevenar 13 will be done through:

- Computation of the asymptotic standardized 95% CI on the difference between the percentages of subjects with antibody concentrations and OPA titers above proposed cutoffs between the vaccine groups Co-ad and (minus) PCV13 (Visit 2).
- Computation of the 95% CI of the GMC and GMT ratios between the Co-ad and (over) the PCV13 vaccine groups (Visit 2). This will be performed using an ANCOVA model on the \log_{10} transformation of the concentrations/titers using the prevaccination \log_{10} transformation of the concentrations or titers, the country, the number of doses of Prevenar 13 received before the study (2 or 3 doses), and the vaccine group as covariates.

An exploratory evaluation of the comparability of the immune response to each meningococcal group at 1 month after the first dose of MenACWY-TT and at 1 month after the second dose of MenACWY-TT will be done through:

- Computation of the asymptotic standardized 95% CI on the difference between the percentage of subjects with rSBA and hSBA titers above proposed cutoffs between the ACWY2d vaccine group (after the second dose of MenACWY-TT, Visit 4) and (minus) the ACWY1d vaccine group (Visit 2).
- Computation of the 95% CI of the rSBA and hSBA GMT ratios between the ACWY2d vaccine group (after the second dose of MenACWY-TT, Visit 4) and (over) the ACWY1d vaccine group (Visit 2). This will be performed using an ANCOVA model on the \log_{10} transformation of the titers using the prevaccination \log_{10} transformation of the titers, the country, the number of doses of Prevenar 13 received before the study (2 or 3 doses), and the vaccine group as covariates.
- These analyses will be performed on the adapted ATP cohort.

6.1.3. Analysis Of Safety

The primary analysis will be performed on the total vaccinated cohort. If, for any vaccine group, more than 5% of the enrolled subjects are eliminated from the ATP cohort for safety, then a second analysis will be performed on the ATP cohort for safety to support the analyses of the total vaccinated cohort.

All percentages/proportions described below will be tabulated with exact 95% CIs.

Timing between reconstitution of and vaccination with MenACWY-TT will be summarized per vaccine group and overall.

The percentages of subjects with at least 1 local event (solicited and unsolicited), with at least 1 general event (solicited and unsolicited), and with any event or AE during the 4-day solicited follow-up period will be tabulated. The same calculations will be performed for events rated as Grade 3 and for events related to vaccination.

The percentage of subjects reporting each individual solicited local (any grade, Grade 3, and requiring medical advice) and general (any grade, Grade 3, related, Grade 3 and related, and requiring medical advice) event during the 4-day follow-up period (Day 0 – Day 3) after vaccination will be tabulated. Occurrence of fever will also be reported per 0.5°C cumulative increments up to >40.0°C. All of the above calculations will also be performed by country and by the number of doses of Prevenar 13 received before the study (2 or 3 doses).

The percentages of subjects using concomitant medication (any medication, any antipyretic, any antipyretic taken prophylactically, respectively) during the 4-day and 31-day follow-up periods (Day 0 – Day 3 and Day 0 – Day 30, respectively) after each vaccination will be summarized.

The verbatim reports of unsolicited AEs will be reviewed by the medical monitor and the signs and symptoms will be coded according to MedDRA terminology.

The percentages of subjects with unsolicited AEs within 31 days after vaccination (Day 0 – Day 30) will be tabulated by vaccine group and by MedDRA preferred term. Similar tabulations will also be performed by country and by the number of doses of Prevenar 13 received before the study (2 or 3 doses). Likewise, tabulations by vaccine group and MedDRA preferred term will also be done for Grade 3 unsolicited AEs, for unsolicited AEs possibly related to vaccination, and for Grade 3 unsolicited AEs possibly related to vaccination.

SAEs, withdrawals due to AE(s), and large swelling reactions will be described in detail. Similar calculations will also be performed by country and by the number of doses of Prevenar 13 received before the study (2 or 3 doses).

The numbers and percentages of subjects with SAEs and NOCIs (eg, autoimmune disorders, asthma, type 1 diabetes, and allergies) will be tabulated with exact 95% CIs by vaccine group. Similar calculations will also be performed by country and by the number of doses of Prevenar 13 received before the study (2 or 3 doses).

6.2. Analysis Of Persistence

6.2.1. Demography

Demographic characteristics (age [in months, with range and SD] at Years 1, 3, and 5, sex, geographic ancestry, ethnicity, and months since the last dose of vaccine) for each study cohort will be tabulated per vaccine group.

The distribution of subjects enrolled at Years 1, 3, and 5 among the study sites will be tabulated as a whole and per vaccine group and the reasons for not attending a visit at Years 1, 3, and 5 among all vaccinated subjects will be summarized.

The following demographic analyses will also be performed overall and by country and by the number of doses of Prevenar 13 received before the study (2 or 3 doses):

- Demographic characteristics (age [months] at Visit 1 given that the subject attended Year X, age [in months, with range and SD] at Years 1, 3, and 5, sex, geographic ancestry, ethnicity, and months since the last dose of vaccine) will be tabulated per vaccine group for the ATP cohort for persistence.
- Distribution of subjects among study sites.
- Reasons for not attending Year X.
- Summary of subjects enrolled into the study and excluded from ATP analyses along with reasons for exclusion.

6.2.2. Analysis of Persistence at Year 1, 3, and 5

For each Year 1, 3, and 5: the analysis of antibody persistence will be based on the ATP cohort for persistence for that year. If for any vaccine group, at any time point, the percentage of subjects with serological results excluded from the ATP cohort is higher than 5%, a second analysis based on the total cohort (ie, total cohort Year X) will be performed to complement the ATP analysis.

6.2.2.1. Within-vaccine-group Analysis

For the ACWY1d, ACWY2d, Co-ad, and PCV13 vaccine groups for each antigen assessed at each blood sampling time point:

- Percentages of subjects with rSBA-MenA, rSBA-MenC, rSBA-MenW-135, and rSBA-MenY titers $\geq 1:8$ and $\geq 1:128$ will be calculated.
- Percentages of subjects with hSBA-MenA, hSBA-MenC, hSBA-MenW-135, and hSBA-MenY titers $\geq 1:4$ and $\geq 1:8$ will be calculated.
- GMTs with 95% CIs will be calculated.

- The distribution of antibody titers will also be tabulated and evaluated using reverse cumulative distribution curves.

In addition to the overall analyses, the following analyses of persistence on the ATP cohort for persistence at Year 1, 3, and 5 will also be performed by country and by the number of doses of Prevenar 13 received before the study (2 or 3 doses):

- Percentages of subjects with rSBA-MenA, rSBA-MenC, rSBA-MenW-135, and rSBA-MenY titers $\geq 1:8$ and $\geq 1:128$ will be calculated.
- Percentages of subjects with hSBA-MenA, hSBA-MenC, hSBA-MenW-135, and hSBA-MenY titers $\geq 1:4$ and $\geq 1:8$ will be calculated.
- GMTs with 95% CIs will be calculated.

6.2.2.2. Modeling Prediction

In order to complement the descriptive analyses of observed persistence per time point, longitudinal analyses will be performed after Year 5 for rSBA-MenA, rSBA-MenC, rSBA-MenW-135, and rSBA-MenY. These analyses will include all results from Month 0 up to Year 5 and will be performed on the adapted ATP cohort.

A longitudinal model taking into account the vaccine group and all available immunogenicity time points from the beginning until the last time point will be fitted. This model will be primarily aimed at evaluating the selection effect in the vaccine group. Time points will be considered as categorical.

For a specific assay, the model will include assay results from a time point provided that these were part of the ATP cohort for that time point. Results below cutoff will be set at half the value of the cutoff. The model will be fitted via the proc mixed procedure according to the following code:

```
Model 1 - Repeated model on all available time points
PROC MIXED data=sero ;
CLASS group time;
MODEL log_val = group | time ;
  Repeated time / TYPE=UN SUBJECT=pid;
RUN;
```

Per [Section 10.7.3](#) of the protocol, “a longitudinal analysis will be performed after Year 5. These analyses will include all results from Month 0 up to Year 5 and will be performed on the ATP cohort for immunogenicity adapted per time point and the ATP cohort for persistence at Year 1, 3, and 5, respectively.” So the modeling prediction will also be performed for the ATP cohorts for persistence at Years 1, 3, and 5. The analysis of the ATP cohort for persistence at Year X will include data from Year >X if available for eligible subjects. These analyses will be performed only after Year 5.

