##### **5.2.2.2.1. Study Group and Treatment Number Allocation**

The target will be to enrol approximately 800 eligible subjects who will be randomly assigned to one of the four study groups in a (1: 1: 1: 1) ratio (approximately 200 subjects in each group).

Allocation of the subject to a study group at the investigator site will be performed using a randomisation system on the Internet (SBIR). The randomisation algorithm will use a minimisation procedure accounting for centre, country and number of doses of *Prevenar 13* received before the study start (2 or 3 doses). Minimisation factors will have equal weight in the minimisation algorithm.

After obtaining the signed and dated ICF from the subject's parent(s)/LAR(s) and having checked the eligibility of the subject, the site staff in charge of the vaccine administration will access SBIR. Upon providing the subject identification number, the randomisation system will determine the study group and will provide the treatment number to be used for the first dose.

The number of each administered treatment must be recorded in the eCRF on the Vaccine Administration screen.

When SBIR is not available, please refer to the SBIR user guide or the Study Procedures Manual (SPM) for specific instructions.

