### 10.3. Determination of Sample Size

The target sample size is 640 evaluable subjects (160 in the 4 study groups) for the statistical analysis of epoch 001. Considering that approximately 20% of the enrolled subjects might withdraw or not be evaluable for immunogenicity post-vaccination, the target sample size to be enrolled is 800 subjects (200 in each study group).

Moreover, assuming 10% drop-out for each persistence visit:

Around 576 subjects will be evaluable at Visit 5 (144 in each study group);

Around 516 subjects will be evaluable at Visit 6 (129 in each study group);

Around 468 subjects will be evaluable at Visit 7 (117 in each study group).

The co-primary confirmatory objectives will be assessed in a hierarchical manner according to the order presented below. A co-primary objective can only be met if the statistical criteria for that objective are met as well as the statistical criteria for all previous co-primary objectives. Therefore, the multiplicity of objectives does not require an alpha adjustment. However, it impacts the beta as the last objective can only be reached if the last and all previous objectives are met simultaneously.

**Confirmatory primary objective 1:** To demonstrate non-inferiority of meningococcal conjugate vaccine MenACWY-TT when co-administered with 13-valent pneumococcal vaccine *Prevenar 13* versus meningococcal conjugate vaccine MenACWY-TT given alone.

*Criterion for non-inferiority of the meningococcal serogroups A, C, W-135 and Y.*

Non-inferiority will be demonstrated for each serogroup separately if the lower limit of the two-sided standardized asymptotic 95% CI for the group difference between the Co-ad group and the Pool1d group (Co-ad group minus Pool1d group) in the percentage of subjects with rSBA-MenA, rSBA-MenC, rSBA-MenW-135 and rSBA-MenY  $\geq 1:8$  is greater than or equal to -10%.

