### **10.7.3. Modelling Prediction**

In order to complement the descriptive analyses of observed persistence per timepoint and minimize the bias that may have occurred due to the loss to follow-up after the vaccination, a longitudinal analysis will be performed after Year 5 for rSBA-MenA, rSBA-MenC, rSBA-MenW-135 and rSBA-MenY. These analyses will include all results from Month 0 up to Year 5 and will be performed on the ATP cohort for immunogenicity adapted per timepoint and the ATP cohort for persistence Year 1, 3 and 5, respectively.

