7.4. Methodology for Computing CI

- All CIs computed will be 2-sided 95% CIs.
- The exact 95% CIs for a proportion within a group will be based on the method by Clopper and Pearson (Clopper and Pearson, 1934).¹
- The standardized asymptotic 95% CI for the group difference in proportions will be based on method 6 described by Newcombe (Newcombe, 1998).²
- The 95% CI for GMTs/GMCs will be obtained within each vaccine group separately. The 95% CI for the mean of log-transformed titer/concentration will be first obtained assuming that log-transformed values were normally distributed with unknown variance. The 95% CI for the GMTs/GMCs will then be obtained by exponential transformation of the 95% CI for the mean of log-transformed titer/concentration.
- The 95% CIs of the vaccine group GMC/GMT ratios will be computed using an ANCOVA model on the logarithm₁₀ transformation of the concentrations/titers. The ANCOVA model will include the prevaccination logarithm₁₀ transformation of the concentration/titers, country, number of doses of Prevenar 13 received before the study (2 or 3 doses), and vaccine group as covariates.

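### The longitudinal model meant to limit loss-to-follow-up bias omits country and prior Prevenar 13 doses, and the persistence percentages have no analysis that uses children who later left

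*SAP*

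**What the plan says.** Protocol 10.7.3 plans a longitudinal analysis after Year 5 for the four rSBA titres, partly to "minimize the bias that may have occurred due to the loss to follow-up after the vaccination". SAP 6.2.2.2 words the aim differently: "This model will be primarily aimed at evaluating the selection effect in the vaccine group". The only code given has "CLASS group time", "MODEL log_val = group | time" and "Repeated time / TYPE=UN SUBJECT=pid". The response is log titre, and time is categorical from Month 0 to Year 5.

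Protocol 5.2.2.2.1 states: "The randomisation algorithm will use a minimisation procedure accounting for centre, country and number of doses of" Prevenar 13 (2 or 3). SAP 6.1.2.2 and 7.4 fit every GMC or GMT ratio by an ANCOVA with the prevaccination value, "country, number of doses of Prevenar 13 received before the study (2 or 3 doses), and vaccine group as covariates".

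SAP 4.1 lists the percentages with rSBA ≥1:8 and ≥1:128, and the GMTs, at Years 1, 3 and 5 in ACWY1d and ACWY2d as primary endpoints. They serve an exploratory primary objective (SAP 3.1.1). Missing immunogenicity values are left missing (SAP 7.1.1). The Total Cohort Year X holds only children who return (SAP 5.5). The analysis on it is triggered by ATP exclusions among children who have results (SAP 6.2.2).

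**The concern.** A likelihood-based repeated-measures model corrects for drop-out only through what it contains: here the group, the time point and the child's own observed titres. If country, or the number of prior doses, affects both who stays and later titre beyond what that history shows, some bias remains in the group means. Both factors are known for every child, and the SAP already adjusts for them elsewhere. No reason is given for leaving them out of the one model aimed at drop-out.

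The second gap does not depend on country. The model yields means of log titre and nothing for the ≥1:8 and ≥1:128 rates. Even where it corrects the GMTs fully, the report would set corrected GMTs beside uncorrected percentages for the same visit. At stake is the accuracy of the within-group five-year persistence estimates, which Protocol 1.2.1 gives as a reason for the study.

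**Working it through.** **1. Planned attrition (Protocol 10.3).** 640 evaluable from 800 enrolled (20% loss), then 10% per persistence visit. 640 × 0.9 = 576.0; × 0.9² = 518.4; × 0.9³ = 466.6. The plan states 576, 516 and 468, so its figures reproduce apart from rounding. Loss by Year 5 is 1 − 468/640 = 26.9% of evaluable children, or 1 − 468/800 = 41.5% of enrolled children.

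**2. Bias in an observed percentage.** Bias = fraction lost × (rate in returners − rate in non-returners). The documents do not give the gap. At 26.9% lost, assumed gaps of 5 and 10 points give 1.3 and 2.7 points. For scale, the largest 95% half-width at n = 117 is 1.96 × √(0.5 × 0.5/117) = 9.1 points.

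**3. What the SAP model leaves in the GMTs.** This is a large-sample illustration; every input is assumed, because the documents give no retention or titre by country.
- Six countries, with Year 5 retention from 45% to 95% rising with the country's mean titre (average 70%, so about 30% lost over three visits).
- Within-country SD 0.9 log10; correlation of Month 1 with Year 5 of 0.4, and 0.6-0.8 among Years 1, 3 and 5.
- The model uses all time points with an unstructured covariance, as in the SAP.

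| Between-country SD (log10) | Observed Year 5 GMT too high by | SAP model, country effect from Month 1 | SAP model, country effect only after Month 1 | Model with country |
|---|---|---|---|---|
| 0.1 | about 6% | about 2% | about 3% | near 0 |
| 0.2 | about 12% | about 4% | about 6% | near 0 |
| 0.3 | about 18% | about 6% | about 9% | near 0 |

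The share left is 2/6 = 4/12 = 6/18 = one third, or 3/6 = 6/12 = 9/18 = one half. The observed ≥1:8 rate is about 1 to 3 points too high over the same range.

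Direction and share depend on the inputs. In a separate run, a two-level factor shifted titres by 0.5 log10 after the first time point, and loss was greater in the high-titre level. The observed GMT was then 0.916 of the truth, the SAP model's 0.945, and 1.000 with the factor included. That bias is downward, and (1 − 0.945)/(1 − 0.916) = 65% of it remains.

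**4. The percentages when the model works.** Let drop-out depend only on the last titre (assumed inputs, 29.7% lost). The SAP model recovers the GMT exactly (ratio to truth 1.00; observed 1.23). The observed ≥1:8 rate is 77.8% against a true 73.8%, and no planned analysis corrects it.

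**5. The comparison between arms.** In a two-arm run with retention by country equal across arms, bias in the two-dose over one-dose GMT ratio was under 0.5%, and in the difference in ≥1:8 rates 0.3 to 0.7 points.

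**The case against.** The strongest reply is that the SAP model already does much of the work. With an unstructured covariance and all results from Month 0 onward, a child's Year 1 and Year 3 titres inform a missing Year 5 value. On the six-country inputs this removes half to two thirds of the GMT bias without country. That stands, so a reader should not infer from the short MODEL statement that most of the bias generally stays. The less favourable run shows that it can, but nothing in the documents says which case applies.

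Allocation is minimised on country and prior doses, so country-driven loss falls about equally on both arms and largely cancels in the one- versus two-dose comparison. That also stands, provided that retention by country does not differ by arm.

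SAP 6.2.1 and 6.2.2.1 tabulate persistence, and reasons for not attending, by country and by prior doses. A country-related distortion could therefore be seen. These tables use observed data only, though, and are not recombined to the starting country mix.

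Finally, these comparisons are descriptive (Protocol 10.8) and the model only complements the observed tables. That limits the weight of the point. It does not explain why known factors are left out, or why the percentages have no counterpart to the modelled GMTs.

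**Conclusion.** The point holds as a cheap improvement to a supportive analysis. The model that Protocol 10.7.3 relies on omits two recorded factors that the rest of the SAP adjusts for. If country drives both retention and titre, about 2-9% bias may stay in the within-group Year 5 GMTs on the six-country inputs, against near zero with country included. The ≥1:8 percentages could be off by about 1-3 points on the same inputs, well inside the 9-point half-width, and no planned analysis corrects them. If country is unrelated to either retention or titre, adding it changes little, but the gap for the percentages remains wherever drop-out follows titre.

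Three stronger readings are not supported:
- That about 42% are lost to follow-up. The first 20% in Protocol 10.3 also covers children who stay but are not evaluable, and some of these can re-enter the persistence cohorts (SAP 5.6). The persistence loss is about 27%.
- That the one- versus two-dose conclusion is materially biased. This would need retention by country to differ between arms, and the documents give no sign of that.
- That a confirmatory result is at risk. Both non-inferiority tests use Visit 2 data and do not involve this model.

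**What to change.** In SAP 6.2.2.2, as a supportive analysis that leaves the planned tables unchanged:

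(a) Add country, country by time, and number of prior Prevenar 13 doses (2 or 3) to the CLASS and MODEL statements of Model 1. Report model means at the country mix of the whole post-dose ATP cohort, not that of returners.

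(b) From the same model, multiply impute missing log titres at Years 1, 3 and 5. Report rSBA ≥1:8 and ≥1:128 by group beside the observed percentages. State that the results are sensitive to the normal model near the assay floor, where values below the cut-off are set to half of it.

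The cost is SAP wording, modest programming and one extra set of supportive tables. No new data are needed, and the model is run only after Year 5.
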